We believe staffing levels are sufficient given the total recruitment target of 10 individuals with SCI and the tasks to be accomplished during the two-year study.

e) Access to target population.

Explain and justify whether you will have access to a population that will allow recruitment of the required number of participants.

We expect to enroll a total of 10 participants with SCI; five individuals in a standard-of-care control group and five individuals in an FES-rowing group. Approximately 35 new patients with SCI are seen per year at the VA Palo Alto Spinal Cord Injury Center. If recruitment from VA Palo Alto proves to be insufficient, we will contact [name] who is the Chief of Spinal Cord Injury, Department of Physical Medicine & Rehabilitation, at the Santa Clara Valley (SCV) Medical Center In San Jose. [name] has agreed to provide consulting assistance as needed on the recruitment of potential participants with spinal cord injuries receiving their medical care at the SCV Medical Center. Approximately 125 new patients with SCI are seen per year at the SCI Rehabilitation Center at SCV Medical Center. Between VAPAHCS and SCV Medical Center, we do not anticipate difficulty in achieving our recruitment target.

f) Access to resources if needed as a consequence of the research.

State whether you have medical or psychological resources available that participants might require as a consequence of the research when applicable. Please describe these resources.

The VA SCI Center provides comprehensive care to patient with SCI on an in- and out-patient basis. There are dedicated physicians, nurses, therapists, and psychologists on staff with extensive experience addressing the medical and mental needs of this patient population. While it is unlikely that there will be research-related events that will require significant medical follow-up, these services are readily available within the facility.

g) Lead Investigator or Coordinating Institution in Multi-site Study.

Please explain (i) your role in coordinating the studies, (ii) procedures for routine communication with other sites, (iii) documentation of routine communications with other sites, (iv) planned management of communication of adverse outcomes, unexpected problems involving risk to participants or others, protocol modifications or interim findings.

1. Purpose

a) In layperson's language state the purpose of the study in 3-5 sentences.

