- g) **Study Endpoint. What are the guidelines or end points by which you can evaluate the different treatments (i.e. study drug, device, procedure) during the study? If one proves to be clearly more effective than another (or others) during the course of a study, will the study be terminated before the projected total participant population has been enrolled? When will the study end if no important differences are detected?**

The goal of this pilot study is to obtain preliminary data for five subjects participating in a 36-week FES-rowing group. Because of the small number of subjects, it is important to acquire data for all subjects and for all time points in order to determine the best estimates for key descriptive statistics including the mean, standard deviation and range of bone density changes. The study will not end until five subjects have completed the 36-week FES-rowing program.

3. Background

- a) **Describe past experimental and/or clinical findings leading to the formulation of the study.**

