- a) **List all standard of care procedures using ionizing radiation (radiation dose received by a subject that is considered part of their normal medical care). List all research procedures using ionizing radiation (procedures performed due to participation in this study that is not considered part of their normal medical care). List each potential procedure in the sequence that it would normally occur during the entire study. More Info**

Identify Week/Month of study	Name of Exam	Identify if SOC or Research
Start of week 0, end of weeks 8, 22 and 36	DXA and pQCT bone density measurements	Research

- b) **For research radioisotope projects, provide the following radiation-related information:**

Identify the radionuclide(s) and chemical form(s).

N/A

Title : Skeletal Health in the Lower Limbs Following Spinal Cord Injury
Approval Period: 01/13/2015 - 09/02/2015

For the typical subject, provide the total number of times the radioisotope and activity will be administered (mCi) and the route of administration.

N/A

If not FDA approved provide dosimetry information and reference the source documents (package insert, MIRD calculation, peer reviewed literature).

N/A

c) For research radiation machine projects, provide the following diagnostic procedures:

For well-established radiographic procedures describe the exam.

Bone density measurements for both the Standard-of-Care group and the FES-rowing group will be performed using Dual energy X-ray Absorptiometry (DXA) and peripheral Quantitative Computed Tomography (pQCT). These scans will take place at VA Palo Alto. Scans will be performed at four time points: baseline (time 0, i.e., at the start of week 1), and at the end of weeks 8, 22 and 36 following baseline. The DXA scans will include a proximal femur scan and a scan starting immediately proximal to the patella and extending proximally 23 cm, ending just distal to the femoral mid-shaft. Those scans will be randomized to one side only. A standard AP spine DXA scan will also be done. The pQCT scans (same side as DXA scans) will entail two image slices in the distal femur (4% and 20% up from the distal limit of the lateral femoral condyle) and three image slices in the tibia (4% and 34% down from the proximal end of the medial tibial plateau and 4% up from the distal end of the tibia, referenced from the distal limit of the tibial subchondral bone at the center of the tibiotalar joint).

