- resting blood pressure higher than 140/90
- a grade 1 or greater, sacral, gluteal or ischial pressure ulcer
- history of low trauma, lower limb fracture since SCI
- renal disease
- current osteomyelitis
- current thrombosis/hemorrhage
- cancer
- other neurological disease (i.e. stroke, peripheral neuropathy, myopathy)
- any implanted electronic device
- active treatment for epilepsy
- regular use of tobacco
- known coronary artery disease
- family history of sudden cardiac death
- current use of cardioactive medications, e.g., for treatment of congestive heart failure or arrhythmia
- current use of medications that can affect bone density and fracture risk including:
 - bisphosphonates
 - parathyroid hormone (PTH) and PTH analogs
 - androgenic steroids
 - estrogenic steroids
 - glucocorticoids
 - anti-epileptics

We will also exclude patients with cognitive impairments that will limit understanding of the nature of the project or understanding of the informed consent process.

- i) **Describe your screening procedures, including how qualifying laboratory values will be obtained. If you are collecting personal health information prior to enrollment (e.g., telephone screening), please request a waiver of authorization for recruitment (in section 15).**

Subjects initially identified as potential candidates by Drs. [name] and [name] or their clinical colleagues at VA Palo Alto or Santa Clara Valley Medical Center, will be given contact information for [name]. Interested patients will be told to contact [name] to find out about the study and ask any additional questions.

- j) **Describe how you will be cognizant of other protocols in which participants might be enrolled. Please explain if participants will be enrolled in more than one study.**

Title : Skeletal Health in the Lower Limbs Following Spinal Cord Injury
Approval Period: 01/13/2015 - 09/02/2015

Patients will be asked during recruitment if they are participating in any other studies. Participants will not be eligible for our study if they are already participating in another research study that uses drugs or exercise to maintain skeletal health.

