5) Lower limb fracture during muscle conditioning, strength testing or FES-assisted rowing: The use of FES to stimulate paralyzed muscles in individuals with SCI has been studied for more than 50 years. Over that 50-year period there have been two reported cases of a fracture related to the use of functional electrical stimulation. One individual fractured their patella and a second individual fractured their lateral femoral condyle. Although the total number of individuals with SCI who have used functional electrical stimulation to exercise the lower limbs is not known, we believe the risk of a fracture is very low given that there have only been two reported fractures in 50 years of FES use. To further reduce the risk of fracture, only participants who have never experienced a low-energy or fragility fracture will be allowed to take part in this study. In addition, we will measure bone density for each participant at the beginning of the study and those measurements will provide us with an initial assessment of the health of each participant's femur and tibia. If we believe a participant's bones are too weak to safely undergo the muscle conditioning and rowing exercise, that participant will be withdrawn from the study.

6) Increase in neuropathic pain to an unacceptable level: Some spinal cord injured individuals suffer from neuropathic pain which can range from a mild tickling sensation to a severe burning sensation. It is not known what effect, if any, electrical stimulation has on this condition. In addition, some individuals with SCI who have some sensation in their thighs may find the electrical stimulation to be uncomfortable or even intolerable. Any participant who finds the electrical stimulation to produce neuropathic pain or sensation that is unacceptable to them will be withdrawn from the study.

7) Increase in spasticity to an unmanageable level: It is not known what effect FES has on the intensity and frequency of spasticity. In other FES-rowing programs, a few participants have had an increase in spasticity, while some participants have had a decrease. In general, spasticity levels should be reduced after a muscle conditioning or rowing session, since the muscles will be fatigued. If a subject experiences increased spasticity to a level that is unmanageable, they will be withdrawn from the study.

The risks of the Radioisotopes/radiation-producing machines (e.g., X-rays, CT scans, fluoroscopy) and associated risks.

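### The scanned leg is drawn at random with no condition that it be measurable, so a leg with an injury-event fracture or metalwork can enter a five-person mean and SD

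*Combined protocol and SAP*

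**What the plan says.** Section 4(c) describes DXA of the proximal femur and of the lower thigh, and adds: "Those scans will be randomized to one side only". The pQCT slices of the distal femur and tibia use that same side. Read naturally, one draw per participant fixes every lower-limb measurement, on both scanners, at weeks 0, 8, 22 and 36. Section 4(c) does not ask whether the leg can be measured, does not provide for the other leg, and does not say what happens to an unusable scan.

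Section 8(h) limits the fracture exclusion to "history of low trauma, lower limb fracture since SCI", and its implant exclusion covers electronic devices only. Section 9(a), item 5, repeated in 9(c), says that "only participants who have never experienced a low-energy or fragility fracture will be allowed to take part in this study". Both groups enter 3 to 12 months after injury. Rowers must also have physician clearance to exercise, meet range-of-motion (ROM) minimums at hip, knee and ankle, and transfer independently. Controls need only transfer safely, with help if necessary.

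Section 2(g) names the product of the study as "key descriptive statistics including the mean, standard deviation and range of bone density changes" and says that "it is important to acquire data for all subjects and for all time points". The target under Access to target population is "five individuals in a standard-of-care control group and five individuals in an FES-rowing group".

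**The concern.** The exclusions are worded by the energy of the fracture and the type of implant. Neither wording reaches a femoral or tibial fracture sustained in the accident that injured the cord, nor a plate, nail or screw. If such a leg is drawn, the density change at the affected site reflects healing or metal as well as disuse loss. The side is then fixed, so later visits do not correct it.

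The mean, SD and range are all sensitive to one value when there are five. Direction matters too. A change pulled toward zero looks like preserved bone in a rower, and narrows the contrast if it occurs in a control. With no rule set in advance, the choice to keep or drop a doubtful scan would be made with the results in view. The criteria that might screen out some cases also differ between the groups being compared.

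**Working it through.** **1. Can an affected leg get through?** Take a participant who broke a femur in the injury event and has a plate.

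- 8(h) fracture exclusion: not met, because the fracture was not low-trauma.
- 8(h) implant exclusion: not met, because the plate is not electronic.
- 9(a) and 9(c) fragility condition: not breached.
- Withdrawal for weak or markedly low-density bone (9(a), 9(c), 9(d)): looks for low readings, so it does not catch a reading raised by metal or callus.
- Clearance and ROM limits: may stop a rower, but do not apply to a control.

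The participant is admissible, and the draw in 4(c) may fall on that leg.

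**2. Influence of one value among five.** The plan gives no alpha, power, SD or precision figure to reproduce; the only planning number is 5 + 5 = 10. Let the other four values have SD s, and let the fifth lie D from their mean.

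- Shift of the group mean from the mean of the four: D/5.
- Sum of squares about the new mean: 3s² + 0.8D². Dividing by 4, SD = sqrt(0.75s² + 0.20D²).
- Share of the sum of squares from the fifth value: 0.8D² / (3s² + 0.8D²). This passes one half when D² > 3.75s², that is, D > 1.94s.

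| D | Mean shift | SD | Share of sum of squares |
|---|---|---|---|
| 1s | 0.2s | 0.97s | 21% |
| 2s | 0.4s | 1.24s | 52% |
| 3s | 0.6s | 1.60s | 71% |
| 5s | 1.0s | 2.40s | 87% |

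**3. How often?** The documents give no rate. If p is the chance that the drawn leg is affected at a scanned site, the chance of at least one such leg is 1 − (1 − p)^n. All values of p below are assumptions.

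| p | n = 5 | n = 10 |
|---|---|---|
| 2% | 10% | 18% |
| 5% | 23% | 40% |
| 10% | 41% | 65% |
| 20% | 67% | 89% |

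**4. Stable metalwork.** The outcome is change within one leg, so metal that stays put partly cancels. Assume a true loss L of 15% or 30%, a baseline reading inflated by a factor k of 1.25 to 2, and s of 5 or 10 points. The observed loss is L/k, so D = L − L/k.

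- Smallest case: L = 15, k = 1.25. D = 3 points, which is 0.6s at s = 5 and 0.3s at s = 10. The mean shifts 0.6 points. The SD is 4.5 at s = 5 and 8.8 at s = 10.
- Largest case: L = 30, k = 2. D = 15 points, which is 3.0s at s = 5 and 1.5s at s = 10. The mean shifts 3.0 points. The SD is 8.0 at s = 5 and 11.0 at s = 10.

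Stable metal therefore biases the change toward zero, and over much of this range it does not dominate the SD.

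**5. Cost of dropping a person afterwards.** The 95% t-interval half-width is t(0.975, n − 1)/sqrt(n) SDs: 1.24 at n = 5 and 1.59 at n = 4. Scanning a clear leg from the start keeps n at 5.

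**The case against.** The best reply is that the rule may exist elsewhere. Section 4(c) answers a radiation-safety question on an IRB form, and section 16 lists a separate VA Proposal that is not among the documents. That is possible, but 4(c) states an operating rule for choosing the leg, and followed as written it has the gap. If the Proposal holds a limb condition, it should be carried into 4(c).

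Second, section 2(g) ties its summaries to the rowers, for whom clearance, ROM limits and independent transfers make an unhealed leg fracture less likely. This stands as a mitigation. It does not deal with a healed or plated leg that moves freely, and it leaves the controls less screened.

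Third, a reader might infer that controls face no screen at all. They do face one: the exclusion list is common to both groups and includes low-trauma fracture and current osteomyelitis, and controls must transfer safely. What they lack is the clearance and ROM criteria.

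Fourth, an artefact is local. A tibial plate does not touch the femoral DXA, and bone formed at the hip does not touch the tibial slices. This is right, and it argues for handling by measurement site rather than by whole limb or whole participant.

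**Conclusion.** The point holds and is worth correcting. The draw has no measurability condition, and the exclusions leave injury-event fractures and non-electronic metalwork admissible in both groups. The influence formula is exact for five values: beyond about 1.94s, one leg supplies more than half the sum of squares. The frequency of such legs, the value of s and the size of D are not in the documents, so the likelihood and magnitude above show ranges and are not estimates.

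Two stronger readings are tempting. One is that an affected leg will dominate the group result. The documents do not support this: stable metal may only pull the change toward zero, and a healing fracture or metal that shifts in the scan field is the case in which dominance is plausible. The other extends the point to the spine ("A standard AP spine DXA scan will also be done"). The documents do not say which vertebrae are analysed or how far any fixation extends, and the study question concerns the lower limbs, so that extension is not made here.

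**What to change.** Amend 4(c), identically for both groups:

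- Before the side is drawn, record for each leg, from history or medical records, any fracture at or since the injury, any metalwork, and any known heterotopic bone in the scan fields.
- Randomise the side only between unaffected legs. If one leg is unaffected, scan that leg.
- If neither leg is clear, or a problem first appears on the baseline images, omit only the affected measurement sites from the primary summary under a rule set in advance. Report individual values, and the summaries with and without those sites.

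The pQCT scout views cannot serve to choose the leg. Section 4(c) places them at the knee and ankle, on the side already drawn, so they show neither the hip nor the opposite leg. Re-imaging the other leg would add to the stated 19.2 microSv. Excluding whole participants is unnecessary and would cut against the wish in 2(g) for complete data.

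The cost is a short addition to 4(c) and an entry on the screening form, with no added scans. The side is no longer random for the few participants with one usable leg, and an occasional site-level value is lost.

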5.1 Device Name : Odstock 4 Channel Stimulator, model # O4CHS

Describe the device to be used.

In this study we will use a 4-channel muscle stimulator. This device is made by Odstock Medical Limited, The National Clinical FES Centre, Salisbury District Hospital, [name]. This device is currently used in research facilities in England, Canada and United States in programs that offer FES-rowing exercise to individuals with spinal cord injuries.

The device is described on the website:

<http://www.odstockmedical.com/products/odstock-4-channel-stimulator-kit>

Manufacturer : Odstock Medical Ltd.

Risk : Non-significant

Y I confirm the above are true.

Rationale for the device being non-significant risk:

The manufacturer of the O4CHS stimulator, Odstock Medical Limited, was formed in 2005 in response to demand by researchers and clinicians for neuromuscular stimulators with features that are not available with other commercial stimulator devices, such as the use of manual trigger. Odstock Medical, has obtained CE mark for all of their stimulation devices for sale and use within the European Union.

The Odstock 4-channel muscle stimulator (model O4CHS) has been used for many years in FES-rowing research studies in England, Canada and the United States. Our research consultants in England who are pioneers of FES-

Title : Skeletal Health in the Lower Limbs Following Spinal Cord Injury
Approval Period: 01/13/2015 - 09/02/2015

rowing programs, and who have helped establish FES-rowing programs around the world, have used this exact 4-channel stimulator with approximately 30 subjects with SCI and have never had a serious adverse event related to the use of the O4CHS stimulator. Researchers at Spaulding Rehab in Boston also have never experienced a serious adverse event related to the use of the O4CHS stimulator. Given the long history of safe use of the O4CHS stimulator in other FES-rowing program we believe this device qualifies as a non-significant risk.

Sponsor of Project

Indicate who is responsible for submitting safety reports to the FDA:

Y The sponsor is a non-STANFORD investigator or group.

Ordering, Storage and Control

To prevent the device being used by a person other than the investigator, and in someone other than a research participant: Confirm that the device will be handled according to the SHC/LPCH policy for Investigational New Devices or as appropriate. If no, please provide an explanation. :

Y Confirm?

b) Please list in the table below all IDE Exempt Devices (Commercial Device used according to label, Investigational In Vitro Device or Assay, or Consumer Preference/Modifications/Combinations of Approved Devices) to be used on participants.

6. Drugs, Reagents, or Chemicals

a) Please list in the table below all investigational drugs, reagents or chemicals to be administered to participants.

b) Please list in the table below all commercial drugs, reagents or chemicals to be administered to participants.

7. Medical Equipment for Human Subjects and Laboratory Animals

If medical equipment used for human patients/participants is also used on animals, describe such equipment and disinfection procedures.

N/A

8. Participant Population

a) State the following: (i) the number of participants expected to be enrolled at Stanford-affiliated site(s); (ii) the total number of participants expected to enroll at all sites; (iii) the type of participants (i.e. students, patients with certain cancer, patients with certain cardiac condition) and the reasons for using such participants.

(i) 10
(ii) 10
(III) Subjects with SCI will be enrolled. Subjects with SCI will be used because these subjects exhibit substantial musculoskeletal atrophy in the lower limbs, the prevention of which is the focus of our research.

b) State the age range, gender, and ethnic background of the participant population being recruited.

Title : Skeletal Health in the Lower Limbs Following Spinal Cord Injury
Approval Period: 01/13/2015 - 09/02/2015

Age range: 18-50 years
Gender: both
Ethnic background: subjects of all ethnicities are eligible

- c) State the number and rationale for involvement of potentially vulnerable subjects in the study (including children, pregnant women, economically and educationally disadvantaged, decisionally impaired, homeless people, employees and students). Specify the measures being taken to minimize the risks and the chance of harm to the potentially vulnerable subjects and the additional safeguards that have been included in the protocol to protect their rights and welfare.**

No potentially vulnerable subjects will be enrolled.

- d) If women, minorities, or children are not included, a clear compelling rationale must be provided (e.g., disease does not occur in children, drug or device would interfere with normal growth and development, etc.).**

Our inclusion criteria specifically allows for the inclusion of women and minorities. Children will not be included since the study is funded by the Department of Veterans Affairs, which does not conduct research using children.

- e) State the number, if any, of participants who are laboratory personnel, employees, and/or students. They should render the same written informed consent. If payment is allowed, they should also receive it. Please see Stanford University policy.**

We do not plan to recruit participants who are VA or Stanford laboratory personnel, VA or Stanford employees, or Stanford students.

- f) State the number, if any, of participants who are healthy volunteers. Provide rationale for the inclusion of healthy volunteers in this study. Specify any risks to which participants may possibly be exposed. Specify the measures being taken to minimize the risks and the chance of harm to the volunteers and the additional safeguards that have been included in the protocol to protect their rights and welfare.**

The study will not include healthy volunteers.

- g) How will you identify participants for recruitment? (E.g., by: chart review; referral from treating physician; response to ad). Attach recruitment materials in Section #16 (Attachments). All Final or revised recruitment materials, flyers, etc. must be submitted to the IRB for review and approval before use. You may not contact potential participants prior to IRB approval. See Advertisements: Appropriate Language for Recruitment Material.**

The identification of potential participants from VA Palo Alto will be facilitated by [name], who is an Attending Physician in the Spinal Cord Injury Service at VA Palo Alto, and by [name], who is the Director of Clinical Research in the VA Palo Alto Spinal Cord Injury Center. In the course of performing their standard clinical responsibilities, both [name] and [name] are in regular contact with inpatients and outpatients in the VA SCI Center. Clinical colleagues of Drs. [name] and [name] whom we will tell about our planned study, will also assist in identifying potential subjects during the course of their standard clinical interactions with patients. A similar situation exists for [name] who is the Chief of Spinal Cord Injury at the Santa Clara Valley Medical Center in San Jose. Any patients who appear to be possible candidates for the study will be told briefly about the study by Drs. [name] and [name], or by their clinical colleagues, and if a patient expresses an interest in the study, they will be given contact information for [name]. Interested patients will be able to ask any additional questions by contacting [name].

- h) Inclusion and Exclusion Criteria.
Identify inclusion criteria.**

Subjects in the rowing groups:
· male and female SCI outpatients or inpatients
· have a T1 to T12, ASIA-A or ASIA-B, spinal cord injury
· be at least 18 year old

Title : Skeletal Health in the Lower Limbs Following Spinal Cord Injury
Approval Period: 01/13/2015 - 09/02/2015

- have their physician's clearance to exercise
- between 3 and 12 months post spinal cord injury
- minimum passive hip flexion range of motion (ROM) from 20 to 100 deg
- minimum passive knee flexion ROM from 20 to 100 deg
- minimum passive ankle ROM from +10 deg (dorsi-flexion) to -15 deg (plantar-flexion)
- currently use a manual wheelchair
- be able to perform independent and safe transfers to and from their wheelchair

Subjects in the control group:

- male and female SCI outpatients or inpatients
- have a C5 to T12, ASIA-A or ASIA-B, spinal cord injury
- be at least 18 year old
- between 3 and 12 months post spinal cord injury
- be able to perform safe transfers to and from their wheelchair, either independently or with assistance

Identify exclusion criteria.

Exclusion Criteria

- pregnant women
- women of childbearing potential not practicing a reliable method of contraception
- women who are post-menopausal
- have mechanical instability of the spine
- resting blood pressure higher than 140/90
- a grade 1 or greater, sacral, gluteal or ischial pressure ulcer
- history of low trauma, lower limb fracture since SCI
- renal disease
- current osteomyelitis
- current thrombosis/hemorrhage
- cancer
- other neurological disease (i.e. stroke, peripheral neuropathy, myopathy)
- any implanted electronic device
- active treatment for epilepsy
- regular use of tobacco
- known coronary artery disease
- family history of sudden cardiac death
- current use of cardioactive medications, e.g., for treatment of congestive heart failure or arrhythmia
- current use of medications that can affect bone density and fracture risk including:
 - bisphosphonates
 - parathyroid hormone (PTH) and PTH analogs
 - androgenic steroids
 - estrogenic steroids
 - glucocorticoids
 - anti-epileptics

We will also exclude patients with cognitive impairments that will limit understanding of the nature of the project or understanding of the informed consent process.

- i) **Describe your screening procedures, including how qualifying laboratory values will be obtained. If you are collecting personal health information prior to enrollment (e.g., telephone screening), please request a waiver of authorization for recruitment (in section 15).**

Subjects initially identified as potential candidates by Drs. [name] and [name] or their clinical colleagues at VA Palo Alto or Santa Clara Valley Medical Center, will be given contact information for [name]. Interested patients will be told to contact [name] to find out about the study and ask any additional questions.

- j) **Describe how you will be cognizant of other protocols in which participants might be enrolled. Please explain if participants will be enrolled in more than one study.**

Title : Skeletal Health in the Lower Limbs Following Spinal Cord Injury
Approval Period: 01/13/2015 - 09/02/2015

Patients will be asked during recruitment if they are participating in any other studies. Participants will not be eligible for our study if they are already participating in another research study that uses drugs or exercise to maintain skeletal health.

- k) Payment/reimbursement. Explain the amount and schedule of payment or reimbursement, if any, that will be paid for participation in the study. Substantiate that proposed payments are reasonable and commensurate with the expected contributions of participants and that they do not constitute undue pressure on participants to volunteer for the research study. Include provisions for prorating payment. See payment considerations**

Subjects in the Standard-of-Care group will receive \$50 after each DXA assessment.

Subjects in the FES-rowing group will receive \$150 after each of three participation milestones as appreciation for their participation, distributed as follows:

- After 8-weeks of participation: \$150
- After 22-weeks of participation: \$150
- After 36-weeks of participation: \$150

We do not consider these payments to be inducements to continue or to influence a subject's desire to withdraw at any point in time. The payments are meant to acknowledge our appreciation for a given subject having achieved key study milestones.

- l) Costs. Please explain any costs that will be charged to the participant.**

No costs will be charged to the participants.

- m) Estimate the probable duration of the entire study. Also estimate the total time per participant for: (i) screening of participant; (ii) active participation in study; (iii) analysis of participant data.**

The duration of the study is expected to be two years. Screening and consenting of each participant is expected to take 1 hour.

Active participation for each subject in the Standard-of-Care group is expected to total 10 hours, associated with four, 2.5-hour visits to VA Palo Alto for DXA and pQCT scans, occurring over a span of 36 weeks.

Active participation in the FES-rowing group is expected to be 10 hours for bone density scans, plus 116 hours for regular sessions of muscle conditioning and FES-rowing, plus 12 hours for motion capture and muscle strength testing. The total time for active participation for the FES-rowing group is expected to be 138 hours, or 17.25 days, occurring over a span of 36 weeks.

9. Risks

- a) For the following categories include a scientific estimate of the frequency, severity, and reversibility of potential risks. Wherever possible, include statistical incidence of complications and the mortality rate of proposed procedures. Where there has been insufficient time to accumulate significant data on risk, a statement to this effect should be included. (In describing these risks in the consent form to the participant it is helpful to use comparisons which are meaningful to persons unfamiliar with medical terminology.)

The risks of the Investigational devices.

This study will use an Odstock 4-channel muscle stimulator (model O4CHS) that has been used for many years in FES-rowing research studies in England, Canada and the United States. This device is powered by a standard, 9-volt battery identical to those used to power a transistor radio or smoke alarm. Our research consultants in England who are pioneers of FES-rowing programs, and who have helped establish FES-rowing programs in several other research laboratories around the world, have used this exact 4-channel stimulator with approximately 30 subjects with SCI and have never had an adverse event related

Title : Skeletal Health in the Lower Limbs Following Spinal Cord Injury
Approval Period: 01/13/2015 - 09/02/2015

to its use. Researchers at Spaulding Rehab in Boston also have never experienced an adverse event related to the use of the O4CHS device. Given the long history of safe use of the O4CHS device in other FES-rowing programs we believe this device qualifies as a non-significant risk.

The Odstock 4-channel muscle stimulator is used during FES muscle conditioning, FES muscle strength testing, and FES rowing.

The risks of the Investigational drugs. Information about risks can often be found in the Investigator's brochure.

None.

The risks of the Commercially available drugs, reagents or chemicals. Information about risks can often be found in the package insert.

None.

The risks of the Procedures to be performed. Include all investigational, non-investigational and non-invasive procedures (e.g., surgery, blood draws, treadmill tests).

Other than the bone density scans for which the risk is described later, there are no other procedures to be performed on the Standard-of-Care (control) group.

For the FES-rowing group, participants will undergo an 8-week, Functional Electrical Stimulation (FES) muscle conditioning program to strengthen the quadriceps and hamstring muscles, followed by a 28-week FES-rowing program. At four time points (0, 8, 22, 36 weeks), participants will perform FES muscle strength testing of the quadriceps and hamstrings.

We have assessed potential risks of these procedures by consulting with other research groups with extensive FES-rowing experience and ongoing FES-rowing programs. Potential risks include the following:

- 1) Soft tissue reaction during FES training
- 2) Muscle strain during muscle conditioning, strength testing or FES-assisted rowing
- 3) Fall during transfer to or from rowing machine
- 4) Serious autonomic dysreflexia during FES training
- 5) Lower limb fracture during muscle conditioning, strength testing or FES-assisted rowing
- 6) Increase in neuropathic pain to an unacceptable level
- 7) Increase in spasticity to an unmanageable level

Based on the experience of other researchers with ongoing FES-rowing programs, only two of the above seven issues have ever occurred. These are: 1) a soft tissue reaction during FES training and rowing; and 2) a muscle strain during FES-rowing. Since those are the only issues experienced in previous FES-rowing projects we will discuss them first.

1) A soft tissue reaction to FES training can be associated with several causes. The first is a local reddening of the skin under the electrodes. This reddening is thought to be due to an increase in blood flow beneath the electrode caused by the electrical stimulation. This reddening typically lasts for less than one hour after stimulation is stopped. This reddening is expected to occur to some degree with all participants in the FES-rowing group.

Reddening may also potentially occur as a result of an allergic reaction to the gel used to adhere the surface electrode to the skin. If reddening of the skin persists for much longer than one hour after removal of the electrode, then an allergic reaction is a possible cause. Our consultants in England who have trained

Title : Skeletal Health in the Lower Limbs Following Spinal Cord Injury
Approval Period: 01/13/2015 - 09/02/2015

approximately 30 individuals to become FES-rowers have never seen a case of an individual who was allergic to the electrode gel, although this remains a potential risk.

The third and final potential skin reaction is reddening suggestive of the initiation of soft tissue breakdown (e.g., a "pressure sore") due to excessive pressure or shear stress. In individuals with SCI, the areas most prone to excessive stress are the sacral, gluteal or ischial regions. This potential for skin breakdown exists for all individuals who utilize a wheelchair or who are bed-bound for prolonged periods. Our consultants in England have never had any participants experience skin breakdown caused by their participation in FES-rowing, although this remains a potential risk.

2) Muscle strain during muscle conditioning, strength testing or FES-assisted rowing: As with participating in any exercise program, there is a risk of experiencing a muscle strain. Based on the experience of other researchers with FES-rowing programs, only two out of thirty FES-rowing participants have ever experienced a muscle strain. Muscle strains have never been observed in the lower limbs. For both participants with muscle strains, the strain occurred in the torso, between innervated and paralyzed muscle. These strains were treated by ceasing FES training for 48 to 72 hours and by the use of ice and over-the-counter analgesics. Neither participant has had a repeat incidence of a muscle strain.

3) Risk of a fall during transfer to or from rowing machine: There is a possibility that a participant may fall while transferring to or from the rowing machine or to or from the table they will lie on while having their bone density scans. The risk of falling can be minimized to a very low level by using safe transfer techniques.

4) Serious autonomic dysreflexia during FES training: Autonomic dysreflexia (AD) is a condition which can occur in people who have sustained a spinal cord injury. Autonomic dysreflexia is more common in individuals with tetraplegia (quadriplegia), but it can also occur in individuals with paraplegia. Autonomic dysreflexia can be brought on by a variety of stimuli, including a full bladder or bowel, a pressure sore or infection, exercise, or by Functional Electrical Stimulation. Possible symptoms of an AD reaction include:

- Severe headache
- Flushing or blotching of the skin above the level of the spinal cord injury
- Profuse sweating, particularly above the level of the spinal cord injury
- Increased blood pressure
- Decreased heart rate

